6.6.3 YSI Retention

All YSI values will be captured and retained in OC-RDC database. However, if the difference between Result A (black) and Result B (white) is greater than ($>$) 5%, the YSI values will not be included in the analysis dataset. The corresponding details in analysis of YSI are as following:

(1) At first, delete observations which were identified as deletion according to “deletion flag” collected in OC-RDC database;

(2) Calculate absolute relative difference between Result A (black) and Result B (white) by the formula: $|\text{Result A (black)} - \text{Result B (white)}| / \text{Result A (black)} * 100\%$. If the ARD% is greater than 5%, then this observation will be deleted.

(3) The mean of Result A (black) and Result B (white) will be used in paired data analysis finally.

6.6.4 Sensor Data Retention

Any sensor data beyond 144 hours of functional life time will be removed from all analysis including functional sensor life time, primary endpoints, secondary endpoints, other accuracy analysis, precision analysis, etc. (For the function sensor life time calculation methods, please see section 7.3.).

6.7 Center Pooling

Data will be pooled for analysis.

6.8 Adjustments for Multiple Comparisons

No adjustments will be made.

6.9 Significance Level and Statistical Analysis Software

For the statistical analysis of the primary endpoint and secondary endpoints, the level of significance will be set at one-sided 0.025. The level of significance of tests performed on other indicators will be set at two-sided 0.05 level (except special cases). SAS® 9.4 statistical software and R3.5.2 are applied for statistical analysis.

7. Indicators and Statistical Analysis Methods

7.1 Subject Disposition

The number of subjects enrolled in the study will be presented by study phase. The reasons for discontinuing prior to study completion will be summarized.

- (1) Subjects Enrolled: Subjects who were enrolled in study.
- (2) Screening Failure: The subject did not meet eligibility criteria on visit 1 and did not enter visit 2: randomization. (Is the subject qualified to be randomized into the study collected in CRF was “No”).
- (3) Randomization: The subject entered visit 2: randomization. (Is the subject qualified to be randomized into the study collected in CRF was “Yes”).
- (4) Subjects entering FST: The subject inserted Enlite Sensor successfully and entered visit 4: FST with YSI. (This item is determined based on the subjects’ YSI information).
- (5) Subjects completing Study: Subjects completing Study: The subject completed the last visit. (This item is determined by the section study exit collected in CRF).
- (6) Subjects discontinuing from study phase: The subject did not complete the last visit. (This item is determined by the section study exit collected in CRF).

7.2 Subject Demographics and Baseline Characteristics

Subject demographics and characteristics, including age, gender, race, ethnicity, medical diagnosis, height, weight, BMI, Type of diabetes, diabetes history, pregnancy test, baseline Hct and baseline A1C will be summarized by descriptive statistics (mean, standard deviation, minimum, median, and maximum) for continuous variables and by counts and percentages for categorical variables.

$$\text{Age} = (\text{Informed Consent Date} - \text{Date of Birth}) / 365.25;$$

$$\text{BMI} = \text{Weight (kg)} / (\text{Height (m)})^2.$$

7.3 Sensor Disposition

The number of Enlite Sensor insertions and Enlite Sensor removals for every subject enrolled in the study will be presented.

A descriptive analysis of Enlite Sensor disposition including Enlite Sensor dislodgement and reasons why it dislodged will be included in the Final Report. Enlite Sensor insertion and removals will be characterized by the following:

- Enlite Sensor location.
- Duration of Enlite Sensor wear by investigational center subject report.
- The number and percentage of Enlite Sensors remaining in place at study end.
- Duration of Enlite Sensor wear (subject report) by insertion site.
- Reason for removal: for example, scheduled removal, AE, fell out.

The functional life of the Enlite Sensor will also be characterized. The duration of Enlite Sensor performance from the time of first valid Interstitial Signal (ISIG) to the last glucose reading (i.e., time to end of Enlite Sensor life) will be described with Kaplan-Meier curves.

For the duration of Enlite Sensor analysis, both the physical sensor life time and functional sensor life time based on sensor level will be provided. The corresponding calculation method are as following:

(1) Physical sensor life time (hours) = (Removal time- Insertion time) /3600, the insertion time and removal time collected in OC-RDC database.

(2) Functional sensor life time (hours): The analysis data collected in iPro2 database. Related calculation method is as following:

- 1) Find the first valid Interstitial Signal (ISIG) value (i.e. first sensor glucose value), and its corresponding time will be considered as beginning time.
- 2) Find the last available Sensor value, and its corresponding time will be considered as ending time.
- 3) Functional sensor life time (hours) = (Ending time- Beginning time) /3600.

7.4 Treatment Characteristics

The total number of YSI collected and deleted will be calculated. In addition, the detailed reason for YSI deletion will also be provided.

7.5 Interim Analyses

Not Applicable.

7.6 Primary Endpoint

For the primary endpoint 20/20% consistency rate analysis, both the analyses based on measurement level and subject level will be provided. One sample T test will be used for the analysis of the primary endpoint based on subject level. Both the approximate normal distribution method and Clopper-Pearson method will be used to estimate primary endpoint based on measurement level. The 95% confidence limit of mean agreement rate will be calculated and tested against corresponding threshold pre-specified in protocol.

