9.6. Replacement Sensors

If subjects have either of the sensors which has dislodged any time prior to YSI FST visit or within a duration of 5 hours YSI FST, subject will be asked to re-insert both sensors. And re-insertion of Enlite Sensors will be done only once.

Any YSI FST with a duration of 5 hours or more before sensor dislodgement will be considered complete and will not need to be rescheduled.

Subjects will be issued replacement Enlite sensors to be inserted at Clinic but at the date and time specified by the Clinic.

Subject will wear the replaced sensors for 6 days and attempt to complete the required YSI FST visit.

Subjects will have their YSI FST visit rescheduled per the original randomized FST Group.

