9.9. YSI FST Instructions

9.9.1. Monitoring During the YSI FST

The frequency of blood draws for YSI FST sampling is dependent on the value of the previous sample, according to the following ranges:

- less than ($<$) 75 mg/dL (4.2 mmol/L); every 5 minutes (3-8 minutes)
- greater than (\geq) 75 mg/L (4.2 mmol/L); every 15 minutes (7-23 minutes)

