9.12.1.2. Unplanned CIP Deviations

Prior approval is not required when a deviation is necessary to protect the safety, rights or well-being of a subject in an emergency or in unforeseen situations beyond the investigator's control (e.g. subject failure to attend scheduled follow-up visits, inadvertent loss of data due to computer malfunction, inability to perform required procedures due to subject illness).

As soon as possible, the implemented deviation or change and the reasons for it, should be submitted as follows:

- Investigator should report the deviation to the medical device clinical trial administration department of the investigational center.
- The medical device clinical trial administration department of the investigational center then report the deviation to:
 - EC for notification/acknowledgement
 - Sponsor

For medically justifiable conditions which preempt a subject's ability to complete a study-required procedure, it may be permitted to report only one deviation which will apply to all visits going forward. This may also apply for other unforeseen situations (e.g. the subject permanently refuses to complete a study required procedure and the data will not contribute to the primary end point analysis). However, prior approval from Medtronic is required for such situations.

Blood glucose range and duration targets:

Blood glucose in the 70 mg/dL (3.9 mmol/L) range and 2 hour duration are targets. It is expected that the investigational centers participating in the study will make their best efforts to reach these targets with the subjects who participate in these FSTs, but the sponsor understands that managing diabetes itself is a challenge, and meeting the target value and duration for all subjects may not always be possible.

In the event that samples are not able to be collected or analyzed for technical reasons (YSI or IV line problems) reasons must be recorded on the YSI Activity Log eCRF. See Section 9.9 for further details on deviations pertaining to YSI blood samples.

Sensor wear:

Protocol deviation will only be given if the subject is told by site to remove sensor pre-maturely before Day 6.

FST timing:

Out of window protocol deviations related to start of FST time will be given only if the patient does not come on the scheduled day of FST.

FST missing samples:

It is noted that collecting YSI FST every 5 – 15 minutes may be challenging. Deviations for missing YSI FST samples will be reported for the following reasons:

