14.9. Statistical Model and Analyses of Primary Endpoint

Sensor values from primary sensor will be compared to YSI plasma glucose values during YSI FSTs. A within 20% mean agreement rate (± 20 mg/dL (1.1 mmol/L) when Reference BG less than or equal to (\leq) 80 mg/dL (4.4 mmol/L) between Enlite Sensor values and YSI plasma glucose values during YSI FST days defined as μ will be evaluated against the null Hypothesis:

$$H_0: \mu \leq 60\%$$

$$H_1: \mu > 60\%$$

- Statistical testing

One sample T test will be used for the analysis of the primary endpoint. The 97.5% lower confidence limit of the mean agreement rate will be tested against corresponding threshold.

- Missing data
No imputation for missing data will be performed.
- Pass/Fail Criteria
The study pass/fail criteria is based on statistical hypothesis of the primary endpoint. If the 97.5% lower confidence limit is greater than 60%, the study will be considered as success.
- Justification for Exclusion of Particular Information from the testing of the Hypothesis
Not Applicable

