7.7 Secondary Endpoints

For the secondary endpoints including:

- a) a mean rate in Zone A+B of Consensus Error Grid between Enlite Sensor values and YSI plasma glucose values during YSI FST days.
- b) a mean rate in Zone A+B of Clarke Error Grid between Enlite Sensor values and YSI plasma glucose values during YSI FST days.
- c) Mean absolute relative difference (MARD) between Enlite Sensor values and YSI plasma glucose values during YSI FST days.

The analyses of a) and b) based on measurement level will be provided. One sample T test will be used for the analysis of c) mean absolute relative difference (MARD) based on subject level. The 95% confidence limit of a), b) and c) will be calculated and tested against corresponding threshold pre-specified in guideline principles.

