7.13 Changes to Planned Analysis

1. Analysis result of Continuous Error Grid will not be provided in statistical analysis report as there is no requirement in CFDA registration technical review guideline.
2. Evaluation of “First calibration SMBG value ranges (40 - 70 mg/dL, 70 – 180 mg/dL and 180 - 400 mg/dL): the numerical Sensor Glucose Value (SGV) accuracy will be evaluated against YSI stratified by the first calibration SMBG value up to the second calibration SMBG.” will not be provided in the analysis report as there is no requirement in CFDA registration technical review guideline.

8. Validation Requirements

Level I or Level II validation are required for analysis output. Level I requires that the peer reviewer independently programs output and then compares the output with that generated by the original Statistical Programmer. Level II requires that the peer reviewer reviews the code; where appropriate, performs manual calculations or simple programming checks to verify the output.

9. Mock Tables, Listings and Figures

See SAP appendix tables, listings and figures.

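### SAP 7.6 adds pooled-pair confidence limits that ignore clustering within subject, and does not exclude them from the 60% test

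*SAP*

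**What the plan says.** Protocol 5.2.1 and 14.9 name one method for the primary endpoint, the one-sample t-test. Protocol 14.9 attaches the success criterion to it: "If the 97.5% lower confidence limit is greater than 60%, the study will be considered as success". Protocol 14.5 and SAP 6.2 size the study on the same test.

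SAP 7.6 provides the agreement rate at two levels. The t-test is assigned to the subject level. For pooled pairs, "Both the approximate normal distribution method and Clopper-Pearson method will be used to estimate primary endpoint based on measurement level". The section closes by saying that the 95% confidence limit of the "mean agreement rate will be calculated and tested against corresponding threshold pre-specified in protocol". That sentence names no level, and the section mentions no allowance for repeated pairs from one subject.

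SAP 7.7 closes with a nearly identical sentence for the secondary endpoints. There, a threshold comparison does apply to rates analysed only on pooled pairs: "The analyses of a) and b) based on measurement level will be provided", where a) and b) are the two error-grid rates.

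SAP 7.13 records two changes from the protocol. One is "Analysis result of Continuous Error Grid will not be provided in statistical analysis report"; the other drops the accuracy analysis by first calibration value. The added measurement-level analyses of the primary endpoint are not listed.

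**The concern.** There are two problems, and the first holds however the closing sentence of SAP 7.6 is read.

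1. **The pooled intervals are too narrow.** The normal and Clopper-Pearson limits are valid for independent binary observations. Here a subject's pairs share one sensor, one calibration history and one session of about 7 hours, so they are correlated. The intervals overstate precision even as supportive output.

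2. **The SAP leaves open which limit is compared with 60%.** Three limits are produced and the testing sentence covers all of them. The report could show a pooled lower limit above 60% beside a t-test that fails, with nothing in SAP 7.6 to say that the pooled limit carries no weight. For a pivotal registration study, this should not be left to inference.

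**Working it through.** **Inputs from the documents.** Threshold 60%, planning mean 0.72, SD 0.32, n = 58 (Protocol 14.5, SAP 6.2). One-sided level 0.025 (SAP 6.9). One session of about 7 hours per subject (SAP 5.1). YSI draws every 15 minutes, or every 5 minutes below 75 mg/dL (Protocol 9.9.1).

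**The plan's own figure.** The normal approximation gives [0.32 × (1.960 + 0.842) / 0.12]² = 55.8, so 56. The documents' t-quantile formula, solved by iteration, gives 58, and the noncentral t gives 80.2% power at 58. The stated sample size is reproduced. It follows only if 0.32 is used as the SD of subject-level agreement rates, and it is read that way below.

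**Pairs per subject, m (assumption).** The documents give no count. From the sampling rules:
- 7 h at 15 min: 28 (base case).
- 5 h at 15 min: 20. Protocol 9.6 states: "Any YSI FST with a duration of 5 hours or more before sensor dislodgement will be considered complete".
- 2 h at 5 min plus 5 h at 15 min: 24 + 20 = 44. Protocol 9.12.1.2 says that a 70 mg/dL "range and 2 hour duration are targets".
- 7 h at 5 min: 84, a ceiling only.

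**Standard errors at a true rate of 60%, m = 28.**
- Pooled, pairs taken as independent: √[0.6 × 0.4 / (58 × 28)] = √(0.24 / 1,624) = 0.0122.
- Allowing for subjects: 0.32 / √58 = 0.0420.
- Design effect: 28 × 0.32² / 0.24 = 11.95, whose square root is 3.46.
- Implied intraclass correlation: (11.95 − 1) / 27 = 0.41.

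**One-sided error if the pooled limit decided.** P(Z > 1.96 / 3.46) = 28.5%. If the SAP's 95% limit were read as one-sided 95%, P(Z > 1.645 / 3.46) = 31.7%.

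**Simulation and range.** Beta-binomial model, n = 58, true rate 60%, SD taken as that of observed subject rates, 20,000 replicates per row:

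| Pairs per subject | SD | Design effect | Analytic error | Normal | Clopper-Pearson | t-test |
|---|---|---|---|---|---|---|
| 20 | 0.32 | 8.5 | 25.1% | 25.5% | 24.8% | 2.9% |
| 28 | 0.32 | 11.9 | 28.5% | 29.4% | 28.9% | 3.0% |
| 44 | 0.32 | 18.8 | 32.6% | 32.8% | 32.5% | 2.9% |
| 84 | 0.32 | 35.8 | 37.2% | 37.9% | 37.7% | 2.9% |
| 28 | 0.20 | 4.7 | 18.2% | 18.2% | 17.6% | 2.7% |
| 28 | 0.15 | 2.6 | 11.3% | 11.9% | 11.2% | 2.8% |

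A separate run of 100,000 replicates for the base case gave 29.1%, 28.6% and 3.0%.

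**Other base-case results.**
- Coverage of the nominal 95% interval: 42.3% (normal) and 42.8% (Clopper-Pearson).
- About a quarter of trials with a true rate of 60% show a Clopper-Pearson limit above 60% beside a failing t-test.
- Observed mean needed to pass: 0.60 + 2.0025 × 0.0420 = 68.4% for the t-test, against 0.60 + 1.96 × 0.0122 = 62.4% for the pooled limit.

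**Effect of clustering the interval.** With a subject-clustered standard error and t on 57 degrees of freedom (0.32 taken as the SD of the true subject rates), the pooled interval rejects in 3.0% of trials and covers 94.8%. Its half-width is 8.6 points against 2.4 unclustered. With m varying from 20 to 44, one-sided error is 3.0% clustered and 31.4% unclustered.

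**The case against.** The strongest reply is that the decision rule is already fixed. The protocol names only the t-test, has an explicit pass/fail item and sizes the study on that test, and SAP 7.13 does not alter it. SAP 7.6 speaks of estimation, not testing, at measurement level, and the threshold it cites is the protocol's, which belongs to the t-test. SAP 7.7 is weaker support than it looks: it points to guideline thresholds and concerns endpoints for which the protocol plans only intervals. All of this makes the intended reading likely, and a false pass would require setting the protocol's criterion aside. It does not make the SAP say so. SAP 7.7 still shows that pooled limits are compared with thresholds elsewhere in the same plan.

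The second reply concerns the inputs. The count of 28 pairs is derived. YSI values lost to the 5% replicate rule or a deletion flag, or left without a matching sensor value, would lower it. The SD of 0.32 comes from a previous study that the documents do not describe. In the beta-binomial model it implies a widely spread population, with about 15% of subjects having true agreement below 20% and about 24% above 90%. It may be a cautious planning value. This is fair, and it is why the range matters: at an SD of 0.15 the error falls to 11–12%, still more than four times nominal.

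Neither reply answers the missing cluster adjustment, which makes the pooled intervals too narrow even as supportive output.

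**Conclusion.** The concern holds and should be fixed before analysis. On any reading of SAP 7.6, the two measurement-level intervals are too narrow: by a factor of about 3.5 with 28 pairs per subject and an SD of 0.32. If either were used for pass/fail, one-sided error would be about 29% under those assumptions. It would be about 25–33% for 20 to 44 pairs at that SD, and about 11–18% for SDs of 0.15 to 0.20 at 28 pairs.

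That decision error is conditional. The protocol's t-test, its criterion and the sample size of 58 are sound and unaffected. The practical risk is a misleading supportive interval, together with an SAP that does not say it carries no weight. Confidence is high on the arithmetic and on the missing adjustment. Whether anyone would use a pooled limit to decide cannot be known from the documents.

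**What to change.** In SAP 7.6:

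- State that the subject-level one-sample t-test, with its 97.5% one-sided lower limit above 60%, is the only pass/fail analysis. Name FAS#2 as its population and PPS as supportive, since SAP 6.3 uses both without ranking them.
- State that the measurement-level rate is descriptive and is not tested against 60%.
- If an interval is shown for that rate, compute it with subject as the cluster, by GEE with a robust standard error or by a bootstrap that resamples subjects. This replaces the plain normal and Clopper-Pearson limits.

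The cost is SAP wording and one changed procedure call, with no new data and no change to the protocol's test. The measurement-level interval becomes wider, with a half-width of about 8.6 points instead of 2.4 under the base-case assumptions.

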7.7 Secondary Endpoints

For the secondary endpoints including:

- a) a mean rate in Zone A+B of Consensus Error Grid between Enlite Sensor values and YSI plasma glucose values during YSI FST days.
- b) a mean rate in Zone A+B of Clarke Error Grid between Enlite Sensor values and YSI plasma glucose values during YSI FST days.
- c) Mean absolute relative difference (MARD) between Enlite Sensor values and YSI plasma glucose values during YSI FST days.

The analyses of a) and b) based on measurement level will be provided. One sample T test will be used for the analysis of c) mean absolute relative difference (MARD) based on subject level. The 95% confidence limit of a), b) and c) will be calculated and tested against corresponding threshold pre-specified in guideline principles.

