14.10. Analyses of Secondary Endpoints

Sensor values from primary sensor will be compared to YSI plasma glucose values during YSI FSTs. And the 95% Confidence Interval of MARD, mean rate in Zone A+B of Clarke Error Grid and Consensus Error Grid will be provided.

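### The Clarke and Consensus Zone A+B rates get only measurement-level confidence limits, which ignore clustering within subjects and are too narrow for the planned threshold test

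*SAP*

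**What the plan says.** SAP 7.7 lists three secondary endpoints: a) the Consensus A+B rate, b) the Clarke A+B rate and c) MARD. For the first two it says "The analyses of a) and b) based on measurement level will be provided". For the third it says "One sample T test will be used for the analysis of c) mean absolute relative difference (MARD) based on subject level". It then adds: "The 95% confidence limit of a), b) and c) will be calculated and tested against corresponding threshold pre-specified in guideline principles". The threshold value is not given. SAP 6.9 sets the level: "For the statistical analysis of the primary endpoint and secondary endpoints, the level of significance will be set at one-sided 0.025".

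SAP 7.6 treats the primary endpoint differently: "both the analyses based on measurement level and subject level will be provided". It also names the interval methods for the measurement level: "Both the approximate normal distribution method and Clopper-Pearson method will be used to estimate primary endpoint based on measurement level". Both of those treat every pair as an independent observation.

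Protocol 14.10 promises only that a 95% confidence interval for MARD and the "mean rate in Zone A+B of Clarke Error Grid and Consensus Error Grid will be provided". It does not state the level of analysis and does not mention a test. SAP 7.13, which lists changes to the planned analysis, does not list the added threshold test. Neither document mentions GEE, a mixed model, a cluster bootstrap or any other variance that allows for repeated pairs within a subject.

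**The concern.** The pairs for these endpoints come from one sensor per subject during one frequent-sampling session of about 7 hours. Consecutive pairs share the sensor, its calibration history and the person, so a sensor that reads badly tends to do so for much of the session. Fifty-eight subjects with 28 pairs each are then worth far fewer than 1,624 independent observations. An interval computed as if they were independent is too narrow, and its lower limit lies too close to the estimate, which favours the device.

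For the primary endpoint the subject-level t test is a valid fallback. For the two error-grid rates there is none: the only interval planned is the doubtful one, and SAP 7.7 uses it for a formal comparison in a report intended for registration.

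**Working it through.** **Inputs from the documents**
- Evaluable subjects: 58 (SAP 6.2).
- Primary-endpoint planning values: null 0.60, alternative 0.72, SD 0.32, one-sided 0.025, power 80% (SAP 6.2).
- One session of about 7 hours per subject (SAP 5.1), sampled every 15 minutes at 75 mg/dL or above and every 5 minutes below (Protocol 9.9.1).
- Pairs per subject: 7 × 60 / 15 = 28, so 58 × 28 = 1,624 pairs.

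**Inputs assumed**
- ICC for A+B from 0.05 to 0.50, because the documents give none.
- True A+B rate of 95% or 90%. The 90% figure is the only A+B benchmark printed (SAP 7.9.3), and it is not said to be the guideline threshold.

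**1. The plan's own sample size.** n = σ²(t_α + t_β)² / (μ₀ − μ_α)², iterated on n − 1 degrees of freedom, gives 57.8, hence 58. Exact power at 58 is 80.2%. With 20% dropout, 58 / 0.80 = 72.5, against the stated 72. The planned size therefore reproduces, and it rests on a subject-level analysis.

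**2. Clustering implied by the planning SD (primary endpoint).** If pairs were independent, the variance of a subject's rate would be 0.72 × 0.28 / 28 = 0.0072. The planned variance is 0.32² = 0.1024.
- Design effect: 0.1024 / 0.0072 = 14.2.
- ICC: (14.2 − 1) / 27 = 0.49. At the null rate of 0.60, the same steps give 0.41.
- Effective number of pairs: 1,624 / 14.2 = 114.
- 95% half-width by measurement: 1.96 × √(0.72 × 0.28 / 1,624) = 2.2 points.
- 95% half-width by subject: t(57) × 0.32 / √58 = 8.4 points.

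**3. Effect on the A+B intervals.** The design effect is 1 + 27 × ICC, and the naive standard error is too small by its square root. At a 95% rate the naive standard error is √(0.95 × 0.05 / 1,624) = 0.54 points. Coverage and error rates come from a beta-binomial simulation with 20,000 replicates per setting.

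| ICC | Design effect | SE ratio | Correct SE (points) | Pooled Clopper-Pearson: coverage | Pooled: lower limit above truth | Subject-level t: coverage | Subject-level t: lower limit above truth |
|---|---|---|---|---|---|---|---|
| 0 | 1.00 | 1.00 | 0.54 | 96.2% | 1.7% | 94.9% | 3.4% |
| 0.05 | 2.35 | 1.53 | 0.83 | 82.0% | 8.6% | 94.1% | 4.9% |
| 0.10 | 3.70 | 1.92 | 1.04 | 71.6% | 14.5% | 92.9% | 6.3% |
| 0.20 | 6.40 | 2.53 | 1.37 | 57.5% | 22.6% | 91.2% | 8.3% |
| 0.30 | 9.10 | 3.02 | 1.63 | 49.8% | 26.4% | 90.7% | 8.8% |
| 0.50 | 14.50 | 3.81 | 2.06 | 40.7% | 31.6% | 89.2% | 10.4% |

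At a true rate of 90%, over ICC 0.05 to 0.50, pooled Clopper-Pearson coverage falls from 80% to 40% and its lower limit exceeds the truth 10.1% to 31.6% of the time. The subject-level t interval covers 94% to 92%, with 4.4% to 7.0% of lower limits above the truth.

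**4. Sensitivity to the number of pairs.** Protocol 9.6 accepts a session of 5 hours as complete, which is about 20 pairs. Coverage of the pooled interval at ICC 0.05 and a 95% rate is then about 85%, still well short of 95%.

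**The case against.** The strongest reply is that SAP 7.7 names no interval method for a) and b). The level of measurement fixes the unit of analysis, not the variance estimator, and a GEE on pairs with subject as cluster would fit the sentence as written. That is correct as far as it goes. But the only measurement-level methods the SAP names, in 7.6, assume independence, and no clustered method appears anywhere. The natural reading is an unadjusted interval. If a clustered one is meant, the SAP has to say so.

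Other points stand in part:
- The pooled percentage of pairs is a legitimate quantity, and the error-grid benchmark is worded in those terms. The fault lies in the interval, not in the point estimate.
- The upper end of the ICC range is borrowed from the 20/20% rate. A+B rates sit near their ceiling and may cluster less. The conclusion does not need that end: at ICC 0.05 the one-sided error is already more than three times nominal.
- The threshold is unseen. The error rates are false-pass rates only if the true rate equals the threshold. With an assumed threshold of 90% and a true rate of 98%, the pooled interval passes about 100% of the time and a clustered one at least 97.5% for ICC up to 0.30, so the decision would seldom change. The reported interval would still be too narrow.
- Protocol 14.9 makes study success depend on the primary endpoint alone.
- Turning the protocol's intervals into tests is a separate inconsistency between the documents. It raises the stakes here but is not itself a clustering fault.

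**Conclusion.** The concern holds. As written, SAP 7.7 leaves two of the three secondary endpoints with no interval that respects the design, and any positive within-subject correlation makes the planned limits err in the device's favour. For 58 subjects with 28 pairs each, the standard error is too small by a factor of 1.5 to 3.8 over ICC 0.05 to 0.50. At a 95% rate, nominal 95% coverage falls to between 82% and 41%.

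These sizes rest on an assumed ICC range, a fixed number of pairs per subject, a beta-binomial model and the reading that the measurement-level methods of SAP 7.6 carry over to 7.7. The direction of the error needs only that reading and a positive ICC. The consequence is confined to secondary claims, so this is something that should be corrected rather than a threat to the success criterion.

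**What to change.** Amend SAP 7.7 so that the 95% intervals for a) and b) treat the subject as the cluster, and name one method in advance. Suitable choices are a logit GEE with subject as cluster and robust variance, a bootstrap that resamples subjects, or Clopper-Pearson on the sample size divided by the estimated design effect. A plain subject-level t interval removes most of the error, but rates near 100% are skewed and it still under-covers (94% down to 89% in the table), so it is better as a supporting analysis.

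Also:
- State whether the target is the pooled percentage of pairs or the mean of the subjects' rates.
- Say what will be reported if no pair falls outside A+B, since GEE and the bootstrap then give no usable interval.
- Keep pooled counts and percentages as description only.
- If the threshold comparison stays, give the threshold value, make the comparison with the clustered interval, and list the test in SAP 7.13 as a change from Protocol 14.10.

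The cost is SAP wording and a different procedure on the same data. No extra subjects or measurements are needed. The intervals will be wider.
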